## 5.6 Adverse Events

An adverse event is defined as any untoward medical occurrence (sign, symptom or laboratory finding), regardless of severity and whether or not attributed to the investigational product. All adverse events, whether observed by an Investigator or Study Coordinator or reported by the Subject, whether related to study drug or not related to study drug, shall be documented on the eCRF and Subject records, together with details, i.e. date of onset, the duration and intensity of each episode, the action taken, the relationship to the investigational product and the degree of severity, the seriousness and the outcome.

## 6 CLINICAL EVALUATIONS

An examination of the Subject's acne will be performed at baseline and at each subsequent visit. During the dermatologic examination, evaluations to determine efficacy of treatment will be conducted, including lesion counts and grading of the Subject's acne using the criteria outlined in the IGA.

Preferably a single Investigator (i.e., Principal Investigator or Sub-Investigator) or qualified staff will perform evaluations of efficacy (i.e., lesion counts and IGA) for each Subject at each visit from the beginning to the end of the Subject's participation to maintain consistency; however, only up to two Investigators or qualified staff may perform evaluations of efficacy for a single Subject if necessary. [*Redacted*].

## 6.1 Lesion Counts and Investigator's Global Assessment

At each visit, an Investigator or qualified staff will assess the Subject's acne by counting the number of open and closed comedones, pustules, papules and nodulocystic lesions. All lesions will be counted, including those present on the nose. An Investigator will also assess the overall status of the Subject's acne vulgaris using the IGA. The IGA scores for each visit will be documented on the eCRF. For the purposes of this study, the face is considered to start at the hairline and end at the jaw line and excludes the eyes, the lips and all mucous membranes. The body is considered as at least one affected area: back, chest and/or shoulders.

## [Redacted]

## Definition of inflammatory and non-inflamatory lesions

| Lesion Type        | Definition   |
|--------------------|--|
| Closed
Comedone | Non-inflammatory lesion; whitehead, skin-colored or slightly inflamed "bump" in the skin   |
| Open
Comedone   | Non-inflammatory lesion; blackhead, surface of the plugged sebaceous follicle has a blackish appearance  |
| Papule             | Inflammatory lesion; a small (≤ 5mm in diameter), solid palpable lesion, usually with inflamed elevation of the skin that does not contain pus |
| Pustule            | Inflammatory lesion; a small (≤ 5mm in diameter), inflamed skin swelling that is filled with pus   |
| Nodules            | Large, hard bumps under the skin's surface   |
| Cysts              | Similar to a nodule, but is pus-filled, and ≥ 5mm in diameter  |

The following scale will be used for the IGA:

## IGA Scale for Acne Vulgaris

| Grade | Description  |
|-------|--|
| 0     | Clear skin with no inflammatory or non-inflammatory lesions  |
| 1     | Almost clear; rare non-inflammatory lesions with no more than one small inflammatory lesion  |
| 2     | Mild severity; greater than Grade 1; some non-inflammatory lesions with no more than a few inflammatory lesions (papules/pustules only, no nodular lesions)          |
| 3     | Moderate severity; greater than Grade 2; up to many non-inflammatory lesions
and may have some inflammatory lesions, but no more than one small nodular
lesion |
| 4*    | Severe; greater than Grade 3; up to many non-inflammatory lesions and may have some inflammatory lesions, but no more than a few nodular lesions                     |

\* The eCRF will allow for reporting of lesion worsening beyond Grade 4 with treatment. Subjects who worsen beyond Grade 4 will be described in the safety evaluation.

Please note that nodulocystic lesions will not be included in the inflammatory lesion count. Counts of nodules and cysts will be reported separately and not included in the inflammatory or non-inflammatory lesion counts.

## 7 STUDY VISITS (SEE STUDY VISIT SCHEDULE)

## 7.1 Visit 1: Baseline (Day 0)

The following procedures will be performed at Visit 1:

1. Written informed consent will be obtained. Subjects who are 18 years of age or older must have provided IRB approved written informed consent. For subjects under the age an assent form for minors must be completed for subjects under the legal age of consent depending on age range required by state laws. Written assent must be accompanied by an IRB approved written informed consent from the Subject's legally acceptable representative (i.e., parent or guardian). Prior to initiating screening for the study, Subjects will be given the approved ICF/assent describing the study and any risks associated with participation. The Subject will be

allowed as much time as needed to read and understand the information presented in the consent/assent form. Appropriate study personnel will be available to answer any questions the Subject might have regarding the study or study-related procedures. If the Subject chooses to participate in the study, he or she will be asked to sign and date the consent/assent form and will be provided with a copy for his or her records. In addition, the Principal Investigator or the Principal Investigator's Designee will provide a HIPAA authorization form (if applicable) for the Subject or the Subject's legally acceptable representative (i.e., parent or guardian) to review and sign. Both the ICF/assent and the HIPAA authorization form (if applicable) must be signed by the Subject or the Subject's legally acceptable representative (i.e., parent or guardian) before any protocol assessments can be undertaken.

2. A complete medical history will be obtained for the Subject's current and past medical conditions. Significant medical history should include, but not be limited to, evidence of hypertension, lipid disorders, obesity\*, heart attack, stroke, congestive heart failure, kidney disease, and auto immune disease and gestational diabetes. Significant surgical history should include, but not be limited to, removal of blockage from an artery and gallbladder removal.

\* Obesity = BMI ≥30 (as defined by Metropolitan Life Insurance Company Chart)

- Demographics and vital signs (blood pressure, pulse, respiratory rate and oral body temperature) will be documented. Subjects must remain in a seated position for 5 minutes before vital signs are obtained.
- 4. A brief physical examination, including height (measured in inches) and weight (measured in pounds), will be performed. At a minimum, the physical examination will include the following: assessment of general appearance, skin, HEENT, heart, lungs, musculoskeletal system, lymph nodes, neurological systems, abdomen, extremities.
- 5. A complete list of current and past (within the previous 30 days) concomitant medications will be obtained for each Subject. (See Section 4.3)
- 6. A urine pregnancy test will be conducted for all females of childbearing potential.
- Lesion counts will be done by counting the number of open and closed comedones, pustules, papules and nodulocystic lesions on the treatment areas. All lesions will be counted, including those present on the nose. (See Section 6.1)
- 8. The overall status of the Subject's acne vulgaris on the treatment areas will be assessed using the IGA. (See Section 6.1)
- 9. Subjects will be evaluated for any signs and symptoms of facial irritation [*Redacted*]. Each Subject will be assigned a severity score based on the Local Irritation Scale. (See Section 5.5)
- 10. When the Subject has completed all screening procedures, compliance with the inclusion and exclusion criteria will be reviewed. After the inclusion and exclusion criteria have been confirmed, the Subject will be randomized to a treatment group. The Subject will be assigned a randomization number (See Section 8.5).
- 11. Pictures of the treatment areas will be collected from designated subjects from Subgroup
- 12. The following will be dispensed during Visit 1:
  - The investigational product

[Redacted]

13. Randomized Subjects will be instructed on the correct method for the application of the Investigational Product. The first application of the Investigational Product will be performed by the Subject at home. The study restrictions will also be reviewed with the Subject and an instruction sheet will be issued to the Subject. (See Section 8.5)

- 14. Randomized Subjects will be provided with a diary and instructed how and when to complete the diary. They will be told that they are to document all treatments administered, including the date and all treatments missed. In addition, Subjects will be instructed to document all AEs. Subjects will also be instructed to call the study site if they experience any severe intolerability (i.e., local skin reactions) to Investigational Product.
- 15. Visit 2 (Day 14 ± 4 days from the date of Visit 1) will be scheduled and the Subject will be instructed to bring all Investigational Product (used, unused, and partially used) and the Subject diary with him or her to this visit.

## 7.2 Visits 2-6: Interim Visits (weeks 2, 4, 6, 8, and 10)

The following procedures will be performed at Visits 2, 3, 4, 5, and 6:

- 1. Lesion counts will be done by counting the number of open and closed comedones, pustules, papules and nodulocystic lesions on the treatment areas. All lesions will be counted, including those present on the nose. (See Section 6.1)
- The overall status of the Subject's acne vulgaris on the treatment areas will be assessed using the IGA. (See Section 6.1)
- 3. The Subject's facial erythema will be assessed. (See Section 6.3).
- 4. Subjects will be evaluated for any signs and symptoms of facial irritation [*Redacted*]. Each Subject will be assigned a severity score based on the Local Irritation Scale. (See Section 5.5)
- 5. Pictures of the treatment areas will be collected from designated subjects from Subgroup
- 6. A urine pregnancy test will be conducted for all females of childbearing potential.
- 7. The occurrence of all AEs will be assessed and documented following procedures in Sections 5.6 and 10.1.
- 8. The use of concomitant medications since the previous study visit will be documented and assessed for each Subject. The use of moisturizer, including the type and how often it has been used, will be included. (See Section 4.4)
- 9. The Subject's compliance with the study protocol, including use and application of Investigational Product, will be assessed. (See Section 8.6) The Subject's diary will be reviewed for completion.
- 10. The following will be dispensed/redispensed:

Visit 2 (week 2):

• The investigational product – redispenced

[Redacted]

Visit 3 (week 4):

• The investigational product – new

[Redacted]

Visit 4 (week 6):

• The investigational product – redispenced

[Redacted]

Visit 5 (week 8):

• The investigational product – new

[Redacted]

Visit 6 (week 10):

• The investigational product – redispenced

[Redacted]

- 11. Study instructions will be reviewed with the Subject, including the procedure for application of the Investigational Product. (See Section 8.5)
- 12. Next visit will be scheduled and the Subject will be instructed to bring all Investigational Product (used, unused and partially used) and the Subject diary with him or her to this visit.

## 7.3 Visit 7: End of Treatment Visit (Week 12; Day 84 ± 4 Days)

The following procedures will be performed at Visit 7:

- 1. Lesion counts will be done by counting the number of open and closed comedones, pustules, papules and nodulocystic lesions on the treatment areas. All lesions will be counted, including those present on the nose. (See Section 6.1)
- 2. The overall status of the Subject's acne vulgaris on the treatment areas will be assessed using the IGA. (See Section 6.2)
- Subjects will be evaluated for any signs and symptoms of the treatment areas irritation [*Redacted*]. Each Subject will be assigned a severity score based on the Local Irritation Scale. (See Section 5.5)
- 4. Pictures of the treatment areas will be collected from designated subjects from Subgroup
- 5. A urine pregnancy test will be conducted for all females of childbearing potential.
- 6. The occurrence of all AEs will be assessed and documented following procedures in Sections 5.6 and 10.1.
- 7. The use of concomitant medications since the previous study visit will be documented and assessed for each Subject. The use of moisturizer, including the type and how often it has been used, will be included. (See Section 4.4)
- 8. The Subject's compliance with the study protocol, including use and application of Investigational Product, will be assessed. (See Section 8.6)
- The Subject's used Investigational Product will be returned to the third-party drug dispenser. (see Section 8.7)

## 7.4 Unscheduled Visits and Early Discontinuation Visit

An Unscheduled Visit is allowed at any time, for any reason, if in the Principal Investigator's opinion it is warranted. If the Unscheduled Visit is due to an AE, the Principal Investigator will determine whether additional visits are needed.

If a Subject is discontinued from the study during an Unscheduled Visit, the Unscheduled Visit will be referred to as an Early Discontinuation Visit and all procedures scheduled for Visit 7 will be performed. If the Unscheduled Visit is not an Early Discontinuation Visit (i.e., the Subject will continue to take part in the study), then all procedures scheduled for that interim visit will be performed, with the exception of the collection of Investigational Product and Subject diaries from Subjects.

If the Subject's condition has worsened to the degree that it is unsafe for the Subject to continue in the study, the Subject may be discontinued from the study as treatment failure and a standard of care treatment may be advised at the Principal Investigator's discretion.

## 8 INVESTIGATIONAL PRODUCT

## 8.1 Description

All study medications will be dispensed by qualified Independent dispenser designated by the Principal Investigator. The investigational product will be dispensed only from the institution(s) specified on FDA Form 1572.

The following treatments will be self-administered or administered by the Subject's caregiver during this study.

The Investigational Product supplied by the Sponsor will consist of the following:

| Test Product:    | [Redacted as ATS55] (Taro Pharmaceuticals U.S.A, Inc.)      |
|------------------|---|
| Placebo Control: | Vehicle of test product (Taro Pharmaceuticals U.S.A., Inc.) |

## 8.2 Storage Conditions

Store at controlled room temperature between  $20 - 25^{\circ}C$  ( $68 - 77^{\circ}F$ ) with excursions permitted to  $15^{\circ} - 30^{\circ}C$  ( $59^{\circ} - 86^{\circ}F$ ).

Protect from freezing.

## 8.3 Packaging, Blinding and Labeling

In order to maintain the study blind the randomization schedule will be generated by a third party. Randomization will be performed according to a computer-generated randomization scheme. The four digit unique randomization number will be designated as the Subject number. Only one Subject number will be assigned to each Subject. The Subject will maintain the same number and treatment assignment throughout the study. [*Redacted*].

## 8.4 Treatment Assignment

The subject study identification number will correspond to a computer-generated randomization schedule assigning that number to one of the three study treatment groups. The randomization scheme will be generated, in blocks of 6, so that the test product and the vehicle (placebo) control are assigned in a 1:1 ratio. The subject numbers at the site will correspond to the order in which subjects are enrolled into the study.

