At Visit 1, an informed consent/assent and HIPAA authorization will be obtained from the potential study Subject before any study procedures take place. After the Subject has been consented/assented, the Subject's medical history will then be documented, including the Subject's concomitant medications. A urine pregnancy test will be performed for female Subjects of childbearing potential. All female Subjects are considered to be of childbearing potential unless they are premenarchal, have been surgically sterilized or have been postmenopausal for at least 1 year. A baseline acne grade will be assigned to the Subject using the Investigator's Global Assessment (IGA) and a baseline lesion count will be performed. The Subject will undergo a brief physical examination, including the recording of vital signs. The Subject will be evaluated for signs and symptoms of local irritation. The Subject will be reviewed against the inclusion/exclusion criteria. Blinded Investigational Product will be dispensed to Subjects who meet all of the inclusion and exclusion criteria using the lowest patient randomization number available at that investigative site. Subjects will be instructed on the application of Investigational Product and completion of Subject diaries. The Investigational Product should not be opened in the clinic. The first application of Investigational Product will be reviewed.

Subjects will return to the study site for visits at Weeks 2, 4, 6, 8, 10, and 12. The Subject's concomitant medications will be reviewed and documented. A urine pregnancy test will be performed for female Subjects of childbearing potential. The Subject will be evaluated for signs and symptoms of local irritation and any adverse events will be documented. The Subject's facial acne will be assessed using the IGA, the Subject's lesions will be counted and these results will be documented. The Subjects are instructed to bring their used Investigational Product and their study diaries to each study visit. Compliance with drug applications will be assessed at each visit. Additional units of Investigational Product will be dispensed and each Subject will receive new diaries during visits at Weeks 2, 4, 6, 8, and 10. In addition, all Investigational Product and diaries will be collected from the Subject during each scheduled visit or the Early Discontinuation Visit.

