## Table 3: Expected Application Site Reactions

[Redacted]

Subjects with a baseline irritation score of 3 (severe, marked/intense) will not be enrolled. After baseline, severe irritation (i.e., grade 3, described as severe or marked/intense) that requires treatment will be reported as an adverse event.

Local irritation reactions in the treatment area are common and the Investigator may instruct Subjects to stop the application of treatment ("rest period") to reduce Subject discomfort and to allow local skin reactions to subside based upon the Investigator's clinical assessment. Treatment should resume as soon as the reaction subsides sufficiently to allow reapplication. All dose modifications must be reported on the appropriate Study Medication Log & Dosing Compliance eCRF.

The treatment period should not be extended beyond 12 weeks due to missed doses or rest periods. Subjects whose condition worsens or lesions do not respond to treatment should be re-evaluated by the Investigator and management reconsidered.

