## 9.3 Randomization and Unblinding Procedures

Subjects will be randomly assigned in a 1:1 ratio to receive the test product or the vehicle (placebo) control. The randomization assignment will be generated using SAS® by an independent statistician, not involved with the study.

The Drug Labeling, Packaging facility will hold the randomization code throughout the conduct of the study in order to minimize bias. A sealed copy of the randomization scheme (as a scratch off portion of the product label attached to the drug accountability page) will be retained at the study site. In the event of an emergency, the Subject-specific treatment may be identified; however, every effort should be made to maintain the blind. Where possible, the CRO medical monitor should be contacted before breaking the blind for any patient. The Sponsor must be notified in the event the blind is broken.

The treatment assignments will remain blinded until the final database is closed.

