## 11.2 Institutional Review Board

Before study initiation, the Principal Investigator must have written and dated approval from the IRB for the protocol, consent form, Subject recruitment materials and any other written information to be provided to Subjects.

Any changes to the protocol as well as a change of the Principal Investigator, which is approved by the Sponsor, must also be approved by the site's IRB and documentation of this approval provided to the Sponsor/designee. Records of the IRB review and approval of all documents pertaining to this study must be kept on file by the Principal Investigator and are subject to inspection during or after completion of the study. All SAEs must also be reported to the IRB.

Periodic status reports must be submitted to the IRB at least annually, as well as notification of completion of the study and a final report within one (1) month of study completion or discontinuation. A copy of all reports submitted to the IRB must be sent to the Sponsor/designee.

The Principal Investigator will ensure that an IRB that complies with the requirements set forth in 21 CFR Part 56 will be responsible for the initial and continuing review and approval of the proposed clinical study.

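### The protocol held at sites prints a single fixed block size of 6, so if blocks are intact within sites any leak of the blind spreads to other subjects in the block (low priority, nearly free to fix)

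*Combined protocol and SAP*

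**What the plan says.** Section 8.4 gives one block size: "The randomization scheme will be generated, in blocks of 6". Allocation there is 1:1, so with two arms each block is 3 test and 3 vehicle. The same section adds: "The subject numbers at the site will correspond to the order in which subjects are enrolled into the study". Section 3 says product is dispensed "using the lowest patient randomization number available at that investigative site".

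Sites hold this text, because under section 11.2 "the Principal Investigator must have written and dated approval from the IRB for the protocol".

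The blind could leak in two ways. Section 9.3 keeps a sealed code at the site, "as a scratch off portion of the product label attached to the drug accountability page", and permits it to be opened in an emergency. Section 5.5 says: "Local irritation reactions in the treatment area are common". An investigator scores irritation (section 5.5), and investigators or qualified staff score lesions and IGA (section 6).

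The safeguards that are visible are a vehicle control, a schedule generated by a third party, a code held by the packaging facility, an independent dispenser, product not opened in the clinic, and contact with the medical monitor before a code break where possible. The visible text has no varying block size and no step to keep the size from sites.

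**The concern.** Concealing the block size is a second line of defence for when a blind leaks. A code break, or a reaction that suggests a treatment, should inform staff about one subject only. Where the block is known to be 3:3 and its boundaries can be counted, the same leak also informs them about the other five.

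All three tested outcomes (inflammatory count, non-inflammatory count, IGA success) are judged by eye. Partial knowledge could therefore affect the scoring of subjects already enrolled. If the inference concerns the next number, it could also affect who is enrolled next.

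**Working it through.** The plan gives no figure to reproduce on this point. The check measures how much a known 3:3 block reveals.

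**Inputs from the protocol.** Block size 6 and 1:1 allocation (8.4); about 300 subjects (9.2); about 5 sites (4.1). That is 300/6 = 50 blocks. With even recruitment (an assumption) it is 300/5 = 60 subjects, or 10 blocks, per site.

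**Assumptions not in the protocol.** Blocks are intact within a site and staff know where each begins. Where reactions are used to guess treatment, each earlier subject's arm is read correctly with probability q. The documents give no reaction rate by arm, so q is varied.

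**1. A few revealed assignments.** Given k revealed in one arm, each other member is in the opposite arm with probability 3/(6 − k):
- k = 1: 3/5 = 60%
- k = 2: 3/4 = 75%
- k = 3: 3/3 = 100%

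**2. Worst case: all earlier assignments known.** There are C(6,3) = 20 orderings of a block.
- The 4th is certain if the first three are in the same arm: 2/20 = 10%.
- The 5th is certain if one arm is used up within the first four: 8/20 = 40%.
- The 6th is always certain.
- Expected certain per block: 0.10 + 0.40 + 1.00 = 1.5 of 6 = 25%, or 75 of 300.
- Expected correct best guesses by position: 0.5 + 0.6 + 0.6 + 0.7 + 0.7 + 1.0 = 4.1 of 6 = 68.3%, against 50% by chance.

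**3. Earlier arms read imperfectly from reactions.** The best guess was enumerated over the 20 orderings and all possible readings.

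| | q = 0.7 | q = 0.8 |
|---|---|---|
| Next subject, average over the block | 54.9% | 57.9% |
| 6th subject, all five others read | 58.5% | 65.4% |

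The average assumes that every earlier subject can already be read. If the most recent subjects cannot, it falls to 53-55% (one unread), 52-54% (two) or 51-52% (three). The first scheduled irritation assessment after baseline is Day 14 ± 4, so some delay is likely; enrolment speed is not given.

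**4. Effect of varying the block size.** Simulated at 60 subjects per site, with an optimal guesser who knows which sizes are in use but not their sequence.

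| Scheme | Certain, all earlier known | Best guess, all earlier known | Best guess, q = 0.7 to 0.8 |
|---|---|---|---|
| Fixed 6 | 25% | 68.3% | 55-58% |
| Mixed 4/6 | about 5% | 69.1% | 54.7-57.7% |
| Mixed 4/6/8 | about 2% | 67.7% | 54.2-56.8% |

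Mixing sizes removes most of the certainty and little of the average predictability. A guesser who does not know the sizes would do worse, and that benefit comes from not disclosing them.

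**The case against.** The strongest case against is that the trial is vehicle-controlled and double-blind, so earlier assignments are not normally known and the block size reveals little. Several stronger readings are tempting, but the documents do not support them.

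- **Investigators can see their position in each block.** Numbers run in order at each site, but no visible text says that whole blocks go to a site or that randomisation is by centre. Section 8.3 ends in a redaction.
- **One code break exposes the rest of the block.** It gives 60/40. Certainty needs three revealed in the same arm or all five others. The code is for emergencies, the sponsor must be told, and section 4.6 removes an unblinded subject from the study.
- **Reactions unmask treatment.** Reactions are called common, but not commoner on test product than on vehicle, and the reaction table is redacted. The 70-80% accuracy is an assumption.
- **The same person scores irritation and efficacy.** Sections 5.5 and 6 permit this but do not state it, and section 6 contains a redaction.
- **A quarter of subjects are exposed.** The 25% needs every earlier assignment to be known.

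It is also fair to say that a scorer who can read treatment from skin reactions learns more from the subject's own skin (70-80% by assumption) than from the block (at most 58-65%, for the 6th subject). No choice of block size closes that route.

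All of this stands and limits the size of the problem. It does not supply a reason to print the block size in a document that sites hold.

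**Conclusion.** The point holds as a low-priority improvement. The printed block size, the use of numbers in site order and the site-held codes are all in the text, and nothing visible varies or withholds the size. Any leak of the blind then spreads further than it needs to: to 60/40 after one revealed assignment, 75/25 after two in the same arm, and certainty after three. Under assumed imperfect reading of reactions the gain to a guesser is modest, 55-58% against 50%, and smaller when recent subjects have not yet reacted.

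This rests on blocks being intact within sites and, for the reaction figures, on an assumed reading accuracy. It does not show that the blind will fail or that the results would be biased by any stated amount. Redacted text may hold further safeguards.

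**What to change.** Delete the block size from section 8.4. Have the independent statistician generate the list with randomly varying block sizes within site, and record the sizes only in a restricted randomisation specification until database lock. Sizes 4, 6 and 8 leave slightly less to infer than 4 and 6.

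The cost is the rewording and regenerating the list. Imbalance at the end of enrolment could reach 3 per site with 4/6, the same as now if blocks are intact within sites, or 4 per site with 4/6/8. If enrolment has begun, the disclosure cannot be undone, and the change is one to carry into the Phase 3 studies.

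The change does not address unmasking from a subject's own reactions.

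While section 8.4 is open, reconcile its phrase "assigning that number to one of the three study treatment groups" with the two-arm design. A block of 6 is 3:3 with two equal arms but 2:2:2 with three.
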